The SALT score is a mathematical approach to the determination of hair loss and hair regrowth.⁶ The percentage of scalp hair loss in each of the sides, back and top of the scalp are determined independently, and are multiplied by the percentage scalp covered in that area of the scalp and the products of each section summed for a final total percentage hair loss, designated as the SALT score. (Appendix 1)

2. Quality of life will be evaluated using the **Alopecia Areata Symptom Impact scale** (AASIS)⁷ and the **Alopecia Areata Quality of Life Index** (AA-QLI).⁸ Safety will be assessed by evaluation of adverse events, physical examinations and laboratory parameters. (Appendices 2 and 3)
3. **SCORing for Atopic Dermatitis (SCORAD) Index** (only applicable to subjects with concomitant AD).⁹

The most widely accepted clinical assessment tool for AD disease severity index is known as SCORAD: This tool combines clinical features of AD such as erythema, dryness, lichenification, percent body surface area, as well as quality of life issues such as pruritus and loss of sleep due to disease. To measure the extent of AD, the rule of nines is applied on a front/back drawing of the patient's inflammatory lesions. The extent can be graded 0–100. The intensity part of the SCORAD index consists of six items: erythema, edema/papulation, excoriations, lichenification, oozing/crusts and dryness. Each item can be graded on a scale 0–

3. The subjective items include daily pruritus and sleeplessness. Both subjective items can be graded on a 10-cm visual analogue scale. The maximum subjective score is 20. All items should be filled out in the SCORAD evaluation form. The SCORAD index formula is: $A/5 + 7B/2 + C$. In this formula A is defined as the extent (0–100), B is defined as the intensity (0–18) and C is defined as the subjective symptoms (0–20). The maximum SCORAD score is 103. (Appendix 4)
4. **The Eczema Area and Severity Index (EASI) score** (only applicable to subjects with concomitant AD):¹⁰ EASI is a validated tool to objectively assess dermatitis severity incorporating surface area involvement. It was designed by modifying the general scheme used in the PASI (psoriasis area and severity index) scoring system, which has been utilized effectively in the assessment of psoriasis. The EASI index assigns proportionate values to 4 body regions (head and neck, 10%; trunk, 30%; upper limbs, 20%; lower limbs, 40%). Each region is assessed separately for erythema, infiltration/papulation, excoriation, and lichenification. The average clinical severity of each sign in each of the 4 body regions is assigned a score of 0 to 3, indicating none, mild, moderate, and severe expression. This percentage of area involved for each of the four body regions is assigned a proportional score from 0 to 6 during the analysis: 0=no eruption; 1=10%; 2=10%–29%; 3=30%–49%; 4=50%–69%; 5=70%–89%; and 6=90%–100%. The buttocks and feet are counted as part of the lower extremities; the internal axillae and groin are counted as part of the trunk; and 3) the external axillae and hands are counted as part of the upper extremities. The total body score for each body region is obtained by multiplying the sum of the severity scores of the four key signs by the area score, then multiplying the result by the constant weighted value assigned to that body region. The sum of these scores gives the EASI total, which ranges from 0 to a maximum 72. (Appendix 5)
5. **Investigator's Global Assessment (IGA) index** (only applicable to subjects with concomitant AD):¹¹ a static IGA score is widely used as a primary efficacy point of treatment success in many studies of dermatological diseases including AD. The static IGA score represents an overall static evaluation of dermatitis, performed by the investigator at each visit. It utilizes a scale of 6-points, ranging from 0 (clear) to 5 (very severe disease), with 0-clear, 1-almost clear, 2-mild disease, 3-moderate disease, 4-severe disease, and 5-very severe disease. IGA scores measure disease severity based on morphology, without referring back to the baseline state. (Appendix 5)

The SCORAD, EASI, and IGA indices will only be undertaken in those subjects who have concomitant AA and AD.

BIOPSY SPECIMENS

The skin site(s) selected for biopsy are anesthetized by injection of 1-2%lidocaine with epinephrine. Two punch biopsies (4.5 mm each; one from involved skin and one from uninvolved skin) prior to initiating study drug and one additional punch biopsy will be repeated at Week 24 or Early Termination Visit (in the vicinity of the involved area

biopsied at Baseline). An optional biopsy will be performed at Week 12 (in the vicinity of the involved area biopsied at Baseline).

Subjects with concomitant AD will have two additional skin biopsies at Baseline (one from involved and one from uninvolved skin), and one additional biopsy at Week 24 or Early Termination visit (in the vicinity of the involved area biopsied at Baseline). An optional biopsy will be performed at Week 12 (in the vicinity of the involved area biopsied at Baseline). All skin biopsies will be 4.5 mm in diameter. The wounds will be sutured and sterile dressings applied. This procedure leaves a small and permanent scar.

The tissue samples will be handled and processed according to the Standard Operating Procedures of the Laboratory for Inflammatory Skin Diseases.

Since this study is designed to gain basic knowledge rather than to yield information directly related to patient care, the results are not entered in the participants' medical records. If, at a later date, correlations of in-vitro tests and the patients' clinical situation suggest that the results do bear on the patients' health, an amended protocol will be submitted to the IRB so that results can be made available to the medical record. As all tissue is obtained for research purposes and not for routine clinical tests, the above outlined blood and skin samples may be stored until used. Skin and/or blood cells will be studied and de-identified samples may be shared with collaborating investigators at Mount Sinai in the future for further histology and immunochemistry, FACS analysis, PCR studies, cell cultures, and gene chip analyses. The samples will be stored indefinitely and will primarily be used for the scope of this study.

LABORATORY SPECIMENS

All blood and urine samples will be processed through the Mount Sinai Center for Clinical Laboratories, [name].

Mechanistic blood analyses including RNA, DNA, and proteomic analysis, as well as ADA will be conducted collaboratively with MedImmune/AstraZeneca.

INSTITUTIONAL REVIEW BOARD

Prior to beginning this study, approval for all study related documents (protocol, consent form, advertising) would be obtained from the Icahn School of Medicine at Mount Sinai Program for the Protection of Human Subjects (Institutional Review Board), [name].

DATA ANALYSES:

This is an exploratory study therefore sample size has been kept relatively low. Data collected from this study will be used to obtain estimates of differences and variability, of the change in treatment for IL-13. If the variability of the Post vs Pre differences are of the magnitude of the LS vs NL differences observed in preliminary data (SE=0.46) then the size of the confidence interval in differences could be observed in this study would be 0.58. As for the secondary outcome, the spontaneous regrowth rate in alopecia areata is 4%. To demonstrate efficacy of the study drug, a response rate of at least 50% is required. To be statistically significant, we would require a minimum of 10 subjects in the study, with an expected response rate of 0 or 1 subject in the placebo group.

MECHANISTIC STUDIES DATA ANALYSES:

For the comparisons of expression levels of lesional, and non-lesional AA skin, we will use RT-PCR, and gene-arrays. RT-PCR values will be normalized to the housekeeping gene hARP (validated in all our AD studies) and log2-transformed prior to analysis. Microarray data will be preprocessed using standard pipeline (exhaustively used by our group in a large number of studies) and log-2 transformed expressions. Adjustments by batch effect and clinical variables will be carried out if needed using ComBat. Mixed effect model on R's *limma* framework will be used and p-values for the moderated t-tests and paired-t-test will be adjusted by Benjamini-Hochberg procedure.

Extensive bioinformatics tools will be employed to gain insights on the results and test hypotheses that are generated in the "data mining stage". This will include (but is not be limited to) pathway and gene-set enrichment analyses using Ingenuity software, GSEA, the R package GSVA (Gene Set Variation Analysis) and other in-house codes produced by our group.

To define cellular and molecular biomarkers of AA in skin biopsies, biomarkers will be divided into those that show significant group differences and those that do not. Multiple regression models will be used to determine the best set of biomarkers that predict disease activity and response. Similar approaches will be carried out for blood analyses.

Gene expression changes in Th2/IL-13, "T22"/IL-22, S100A7 and S100A8, Th1/IFN-gamma, and Th17/IL-17A will be jointly correlated with clinical responses by multivariate analysis using multivariate u-statistics and R package muStat, as we have previously reported.

DATA AND SAFETY MONITORING PLAN

Since this is a phase II study, with few subjects and minimal risks, this project will be monitored by the principal investigator, sub-investigators, and independent DSMB. Both the principal investigator will provide safety data to an independent Data and Safety Monitoring Board every 12 months. This DSMB will be comprised of dermatologists who are not directly related to this study. The DSMB will review all the safety data and provide a report of their findings to the Principal Investigator.

All non-serious events will be reported to the IRB and FDA (on behalf of the IND) on a yearly basis. All serious events will be reported to the IRB and FDA within 24 hours of becoming aware of the event.

Schedule of Events

Formatted: Left: 0.75", Right: 0.75", Top: 1", Bottom: 1", Width: 11", Height: 8.5"

Procedures	Screening (Day -28 to Day -1)	Base-line Day 0	Weeks 2, 6	Week 4	Week 8	Week 10	Week 12	Weeks 14 and 18	Weeks 16 and 20	Week 22	Week 24	Week 32	Week 40	Early Term Visit
Informed consent	X													
Inclusion/exclusion criteria	X	X												
Past Medical History (including demographic data and age on onset)	X													
ECG	X											X		X ⁶
Limited Physical Examination	X						X				X	X	X	X
Vital Signs ¹	X	X	X	X	X	X	X	X	X	X	X			
Chemistry and hematology	X	X		X			X				X	X		X ⁶
PPD or Quantiferon Gold	X													
HIV screening	X													
HBsAg, Anti-HBc antibody	X													
Pregnancy test ²	X	X	X	X	X	X	X	X	X	X				X ⁷
Assessment of Regrowth Pattern	X	X	X	X	X	X	X		X		X	X	X	X
SALT assessment	X	X	X	X	X	X	X		X		X	X	X	X
Subject Questionnaires AASIS and AA-QoL		X		X	X		X		X		X	X	X	X

Procedures	Screen-ing (Day -28 to Day -1)	Base-line Day 0	Weeks 2, 6	Week 4	Week 8	Week 10	Week 12	Weeks 14 and 18	Weeks 16 and 20	Week 22	Week 24	Week 32	Week 40	Early Term Visit
SCORAD, EASI, IGA ³		X		X	X		X		X		X	X	X	X
Blood for mechanistic studies		X					X				X			X ⁷
Blood DNA analysis		X												
Blood RNA and proteomic analysis		X					X				X			X ⁷
ADA measurement		X		X			X				X			X ⁷
Serum drug levels		X		X			X				X			X ⁷
Clinical Photographs		X		X			X		X		X	X	X	X
Scalp Biopsies		X					X ⁸				X			X ⁷
Skin biopsies of atopic dermatitis (AD subset only)		X					X ⁸				X			X ⁷
Study product administration		X ⁴	X ⁴	X ⁴	X ⁴	X ⁵	X ⁵	X ⁵	X ⁵	X ⁵				
Prior and concomitant medication	X	X	X	X	X	X	X	X	X	X	X	X	X	X
Adverse events		X	X	X	X	X	X	X	X	X	X	X	X	X

¹ vital signs will be taken prior to every study drug administration

² Serum pregnancy test for females of childbearing potential at screening and urine test at other visits.

3 These will be performed on subjects with concomitant AD only.

4 For the first four doses of Investigational Product (Baseline, Weeks 2, 4 and 6) subjects will be monitored after IP administration for immediate drug reactions for a minimum of 2 hours with vital signs

 taken every 30 minutes or until stable, whichever is later.

5 For the fifth and subsequent doses of IP, subjects will be monitored after IP administration for a minimum of 1 hour with vital signs taken every 30 minutes or until stable, whichever is later

6 Only if Early Term Visit occurs before Week 32.

7 Only if Early Term Visit occurs before Week 24.

8 Optional biopsies at Week 12.

REFERENCES:

1. Alkhailah A. Alopecia areata update. *Dermatol Clin* 2013;31:93-108.
6. Olsen EA. Investigative guidelines for alopecia areata. *Dermatol Ther* 2011;24:311-9.

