- 3) Percentage change from baseline in the Alopecia Areata Symptom Impact Scale (AASIS) at Week 24.
- 4) Percentage change from Baseline in the Alopecia Areata Quality of Life questionnaire (AA-QoL) at Week 24.

Exploratory endpoints

- 1) Percentage change from Baseline in the objective SCORAD at Week 24.
- 2) Percentage change from Baseline in the EASI score at Week 24.
- 3) Percentage change from Baseline in the Investigator Global Assessment (IGA) score at Week 24, and time points up to Week 24.

INTRODUCTION:

Alopecia areata (AA) is an auto-immune disease characterized by non-scarring hair loss that can sometimes progress to total loss of all scalp and body hair.¹ The life-time risk of AA has been reported to be 1.7%.² AA can cause tremendous emotional and psychosocial distress in affected patients and their families. There is a lack of effective treatments for patients with alopecia areata. Topical treatments are usually not very effective, probably because of limited penetration. Intralesional injections of corticosteroids are effective but can only be considered for patients with limited involvement. Immunotherapy with diphenycyprone or squaric acid dibutyl is effective in some patients but is usually limited to treatment of scalp involvement and can cause significant pruritus and dermatitis. None of these therapies are targeted to the underlying mechanism for disease pathogenesis. There is a need for new treatment options for patients with alopecia areata especially based on the recently evolving understanding of the disorder.

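### Percentage change is a poor metric for the 0-5 IGA: a one-category improvement counts as anything from -20% to -100%, which adds baseline-driven noise in a group of about 10 v 5

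*Combined protocol and SAP*

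**What the plan says.** Exploratory endpoint 3 (OBJECTIVES and ENDPOINTS) is "Percentage change from Baseline in the Investigator Global Assessment (IGA) score at Week 24", and also at earlier time points. EFFICACY EVALUATIONS, item 5, describes the scale: "It utilizes a scale of 6-points, ranging from 0 (clear) to 5 (very severe disease". It adds that "IGA scores measure disease severity based on morphology, without referring back to the baseline state". IGA is scored only in subjects with concomitant AD. STUDY DESIGN expects 15 of these and randomizes them 2:1, separately from the subjects with alopecia areata alone.

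The inclusion and exclusion criteria set no minimum AD severity. Neither DATA ANALYSES nor MECHANISTIC STUDIES DATA ANALYSES names a method, a baseline adjustment or a responder definition for IGA, EASI or SCORAD.

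Exploratory endpoint 1 is "Percentage change from Baseline in the objective SCORAD at Week 24". EFFICACY EVALUATIONS, item 3, prints only the total index, in which "A is defined as the extent (0–100), B is defined as the intensity (0–18) and C is defined as the subjective symptoms (0–20"), and states: "The maximum SCORAD score is 103".

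**The concern.** The IGA numbers label ordered categories, and a ratio of labels has no clinical unit. Dividing by baseline makes a one-step change worth up to five times as much in a nearly clear subject as in a very severe one. The mean percentage change in an arm then depends on who was enrolled as well as on how far they improved. With about five placebo subjects, one or two with low baselines can move that arm's mean appreciably.

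The stake is limited but real. The secondary hypothesis includes better clinical outcomes in subjects with AD, and SCORAD, EASI and IGA are the only AD-specific clinical scores listed.

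**Working it through.** **Inputs from the documents.** IGA 0-5 and SCORAD components A 0-100, B 0-18, C 0-20 (EFFICACY EVALUATIONS); 15 AD subjects at 2:1, so 15 × 2/3 = 10 and 15 × 1/3 = 5 (STUDY DESIGN). The documents give no baseline IGA distribution, so the baseline mixes below are assumptions.

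**The plan's own figure.** Maximum total SCORAD = 100/5 + 7 × 18/2 + 20 = 20 + 63 + 20 = 103, which matches. Without the subjective part C, the maximum is 20 + 63 = 83.

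**One-category improvement as a percentage.** The change from baseline b is -100/b.

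| Baseline to Week 24 | Percentage change | Category change |
|---|---|---|
| 5 to 4 | -20% | -1 |
| 4 to 3 | -25% | -1 |
| 3 to 2 | -33.3% | -1 |
| 2 to 1 | -50% | -1 |
| 1 to 0 | -100% | -1 |

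The order can also reverse: 5 to 3 is -100 × 2/5 = -40%, a smaller value than the -50% for 2 to 1.

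**Noise from chance imbalance.** Suppose every subject in both arms improves by exactly one category, so the arms do not differ. The SD of the arm difference in mean percentage change is SD(-100/b) × √(1/10 + 1/5), and the square root is 0.548. Baseline categories are taken as equally likely.

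| Assumed baselines | Mean of -100/b | SD of -100/b | SD of arm difference |
|---|---|---|---|
| 3-4 | -29.2 | 4.17 | 2.3 points |
| 2-4 | -36.1 | 10.39 | 5.7 points |
| 1-5 | -45.7 | 29.01 | 15.9 points |

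A simulation of 200,000 allocations of 10 v 5 per mix gave the same SDs. The central 95% of arm differences ran from -4.2 to +4.2, from -10.8 to +10.8 and from -29.3 to +32.5 points respectively. Change in category gives an arm difference of exactly 0 in every allocation.

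**Power.** Simulated trials of 10 v 5 used assumed category shifts of -2, -1, 0 and +1, with probabilities 0.45, 0.35, 0.15 and 0.05 on drug and 0.05, 0.20, 0.55 and 0.20 on placebo. With baselines spread over 1-5, t-test power was 47% for percentage change and 57% for category change. With mostly mild or moderate-to-severe baselines, the gain in repeated runs was between 2 and 5 points.

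**The case against.** The case for leaving the endpoint alone has several sound parts.

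- The AD group is randomized separately, so baseline imbalance is random. Percentage change adds noise to the comparison and does not bias it. This stands.
- The wide end of the range needs subjects at IGA 1. At baselines 3-4 the one-step values run only from -25% to -33%. This stands, although the plan does nothing to keep mild subjects out.
- An analysis that used baseline IGA would remove much of the problem. True, but none is stated.
- The power advantage rests on additive shifts, which favour category change by construction. This stands, and the gain should be presented as modest.
- The endpoint is exploratory, carries no power or alpha claim, and the raw categories are recorded anyway. EASI, a 0-72 score, also speaks to AD and is not questioned here.

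A reader might also infer that percentage change is undefined at baseline 0. That is close to hypothetical, because every AD subject is to have a biopsy of involved skin at Baseline, which makes a clear score implausible.

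A reader might further infer that a few mild subjects could decide the direction of the result. The simulations do not support this. Under the assumed effect, the arm difference was tied or had the wrong sign in 3.0% of trials with percentage change and 1.5% with category change (baselines spread over 1-5). The figures were 2.1% v 1.6% (mostly mild) and 1.0% v 1.1% (moderate to severe).

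**Conclusion.** Percentage change is an unsuitable metric for this scale. It gives unequal values to equal steps, can rank a two-step gain below a one-step gain, and adds noise from baseline imbalance with an SD of about 2 to 16 points when all subjects improve equally. The range depends on the assumed baseline mix, on 10 v 5 subjects and on an analysis that ignores baseline. No sample size and no primary or secondary endpoint is affected, so this is a low-cost improvement and not a threat to the trial.

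The stronger reading, that both the IGA and the SCORAD endpoints misstate the treatment effect, is not supported. For IGA the consequence is noise. For SCORAD the documents lack only a printed formula. The endpoint is named objective, the text separates extent and intensity from the subjective symptoms, and the title of the cited SCORAD reference lists the objective SCORAD as an index of its own. Nothing says the total will be analysed under the objective label. That the objective score omits C is inferred from the plan calling C subjective.

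**What to change.** Reword exploratory endpoint 3 as change from Baseline in IGA category at Week 24 and at the earlier AD scoring visits. State one analysis in advance: a rank or ordinal method, or a model with baseline IGA as covariate. Category change still has a floor, since a subject at 1 can gain only one step, so baseline IGA should be tabulated by arm in any case.

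In the SCORAD description, add that the objective SCORAD is A/5 + 7B/2, with a maximum of 83.

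The cost is two lines of wording and no new data, because the IGA category, A and B are already collected. The downside is that IGA will no longer be on the same percentage scale as EASI.

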Fig 1. Figure 1 shows comparable cytokine expression of the defining Th2 cytokine/IL-13, the defining Th1 cytokine/IFN gamma, and the Th17/IL-23 cytokines/IL-17A and IL12/23p40 in AA and AD. Lesional psoriasis skin tissues show a significantly higher expression of both IL-17A and IFN gamma, with significantly lower expression of IL-13 as compared with both AA and AD. Significant decreases in mRNA expression of IL-13, and IL12/23p40 are seen after treatment with intralesional corticosteroids, without significant changes in the other cytokines. P value= 0.0002 for the IL-13, and p=0.1 for the IFN gamma lesional vs non-lesional alopecia skin comparisons. JAK3 shows similar activation in AA, AD, and Psoriasis. NL- non lesional skin from scalp of AA patients; L- lesional skin from scalp of AA patients; PTX- post intralesional steroid treatment skin from scalp of AA patients; PS-psoriasis lesional skin; AD- AD lesional skin. N=6 patients for both NL and L, and 4 for PTX.

STUDY DESIGN:

This is a randomized, double-blind, placebo-controlled pilot study of a total of 30 subjects with moderate to severe alopecia areata involving 30-100% of the scalp. We expect 50% of these subjects to have concomitant alopecia areata (AA) and atopic dermatitis (AD).

Subjects with AA alone (15 subjects) will be randomized (2:1) to either receive tralokinumab 300 mg (150 mg/ml) or placebo via subcutaneous injection using 2 pre-filled syringes Q2W for 24 weeks. Subjects with concomitant alopecia areata and atopic dermatitis (15 subjects) will be randomized separately in a 2:1 ratio to receive tralokinumab 300 mg (150 mg/ml) or placebo via subcutaneous injection using 2 pre-filled syringes Q2W for 24 weeks.

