After providing informed consent, subjects will be assessed for study eligibility at the Screening visit (day -28 to day -1), which includes: limited physical examination (including vital signs); assessment of regrowth pattern; SALT scoring; electrocardiogram (ECG); review of medical history and concomitant medications as well as prior medications/treatments; and serum pregnancy test (if applicable). Laboratory tests will be performed for Complete Blood Count (CBC with differentials (basophils, eosinophils, lymphocytes, monocytes, neutrophils), serum chemistry (albumin, alanine aminotransferase (ALT), alkaline phosphatase (ALP), aspartate aminotransferase (AST), creatinine, potassium, sodium and total bilirubin), as well as hepatitis B surface antigen (HbsAg), hepatitis C antibody, and undergo testing for human immunodeficiency virus (HIV). Subjects will also undergo tuberculin purified protein derivative (PPD) or QuantiFERON TB-Gold test (QFT) testing.

Subjects who meet eligibility criteria (meeting all inclusion and exclusion criteria) will undergo Baseline / Day 0 assessments. These assessments include vital signs, assessment of regrowth pattern, SALT scoring, questionnaires (AASIS and AA-QoL), clinical photography, urine pregnancy test (if applicable), and blood collection for chemistry, hematology, mechanistic studies, DNA analysis, RNA analysis, proteomic analysis, anti-drug antibody (ADA) measurement, and serum tralokinumab levels. In addition, SCORAD, EASI and IGA scores will be performed in subjects with AD only. Two scalp biopsies will be obtained (one from an involved area of the scalp and one from an uninvolved area). Subjects with concomitant AD will have two additional skin biopsies (one from involved skin and one from uninvolved skin). Concomitant medications and any adverse events will be assessed.

Subjects will then undergo randomization, and will receive the first dose (300 mg SC) of study drug (tralokinumab or placebo). Subjects will continue to receive bi-weekly injections of study drug (300 mg tralokinumab or placebo) through Week 24.

Subjects will return for visits every two weeks to have the following performed: vital signs will be taken prior to every study drug administration; concomitant medications and any adverse events will be assessed; and a urine pregnancy test will be performed (if applicable).

For the first four doses of Investigational Product (IP), subjects will be monitored after IP

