If a subject is being discontinued prior to Week 24, the following procedures should be performed for the Early Termination visit: limited physical examination, pregnancy test (if applicable), assessment of regrowth pattern, SALT scoring, AASIS, AA-QoL, SCORAD, EASI and IGA scores (in subjects with AD only), clinical photography, assessment of concomitant medications, assessment of adverse events, and blood tests for chemistry and hematology, mechanistic studies, RNA, proteomic analysis, anti-drug antibody (ADA) measurement, and serum tralokinumab levels. In addition, biopsies of the scalp (one biopsy close to the area that was biopsied at Baseline) and skin (in subjects with AD only, one biopsy close to the area that was biopsied at Baseline) will be performed.

If a subject is being discontinued prior to Week 40 (but has completed Week 24), the following procedures should be performed for the Early Termination visit: limited physical examination, ECG (if not completed at Week 32), assessment of regrowth pattern, SALT scoring, AASIS, AA-QoL, SCORAD, EASI and IGA scores (in subjects with AD only), clinical photography, assessment of concomitant medications, assessment of adverse events, and blood tests for chemistry and hematology.

Subjects will not receive any other active treatment for alopecia areata or atopic dermatitis (outside of the study drug) while participating in the study.

Safety, laboratory, and clinical assessments will be performed at specified clinic visits. A

serum pregnancy test will be performed at Screening and urine pregnancy tests will be performed at Baseline and every 2 weeks prior to administration of the IP dose, if applicable.

Biopsies from the scalp will be performed on all subjects at Baseline and Week 24 or Early Termination visit. At Baseline, biopsies will be obtained from involved and uninvolved areas of the scalp. At Week 24 or Early Termination visit, the biopsy will be performed in the vicinity of the involved area biopsied at Baseline. An optional biopsy will be performed at Week 12, close to the area that was involved and biopsied at Baseline.

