2. Subject has provided written informed consent prior to any study specific procedures.
3. Body weight of ≥ 40 and <150 kg at enrollment.
4. Subject has a history of alopecia areata for at least 3 months.
5. Subject has extensive patchy alopecia areata (at least 30% scalp hair loss).
6. No evidence of hair regrowth at Baseline.

- Women of childbearing potential (WOCBP) (after menarche), including adolescent females, must use a highly effective form of birth control (confirmed by the investigator). Highly effective forms of birth control includes: true sexual abstinence, a vasectomised sexual partner, Implanon, female sterilization by tubal occlusion, any effective intrauterine device/system (IUD/IUS), Depo-Provera injections, oral contraceptive, and Evra Patch or Nuvaring. WOCBP must agree to use highly effective method of birth control, as defined above, from enrolment, throughout the study duration and within 16 weeks after last dose of investigational product (IP), and have negative serum pregnancy test result at Visit 1.

Women not of childbearing potential are defined as women who are either permanently sterilized (hysterectomy, bilateral oophorectomy, or bilateral salpingectomy), or who are postmenopausal. Women will be considered postmenopausal if they have been amenorrheic for 12 months prior to the planned date of randomization without an alternative medical cause. The following age specific requirements apply:

- a. Women <50 years old would be considered postmenopausal if they have been amenorrheic for 12 months or more following cessation of exogenous hormonal treatment and follicle stimulating hormone (FSH) levels in the postmenopausal range.
- b. Women ≥ 50 years old would be considered postmenopausal if they have been amenorrheic for 12 months or more following cessation of all exogenous hormonal treatment.

7. For WOCBP only: have a negative urine pregnancy test prior to administration of the IP.
8. For inclusion in the voluntary pharmacogenetic research, subjects should fulfil the following criterion:

- a. Provision of a signed and dated written informed consent for the pharmacogenetic sample and analysis. If a subject declines to participate in the pharmacogenetic research, there will be no consequence or loss of benefit to the subject. The subject will not be excluded from the other aspects of the study described in the protocol, as long as they consent to participate in the study.

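### Does a population with up to 100% scalp involvement clash with the patchy-disease criterion and the uninvolved-scalp biopsy?

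*Combined protocol and SAP*

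**What the plan says.** The opening of Study Design gives the population as "30 subjects with moderate to severe alopecia areata involving 30-100% of the scalp". Inclusion Criterion 5 words it differently: "Subject has extensive patchy alopecia areata (at least 30% scalp hair loss", with no numeric ceiling and no definition of patchy. The same Study Design section ties entry to the criteria: "Subjects who meet eligibility criteria (meeting all inclusion and exclusion criteria) will undergo Baseline / Day 0 assessments".

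For the Baseline visit, Study Design states: "Two scalp biopsies will be obtained (one from an involved area of the scalp and one from an uninvolved area". The later biopsy paragraph of that section applies scalp biopsies to all subjects and adds: "At Baseline, biopsies will be obtained from involved and uninvolved areas of the scalp". The Biopsy Specimens section repeats the pair as "one from involved skin and one from uninvolved skin) prior to initiating study drug". The Schedule of Events marks the Baseline scalp biopsies without a footnote, and no exclusion criterion mentions total scalp loss.

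The uninvolved sample is used in Mechanistic Studies Data Analyses: "For the comparisons of expression levels of lesional, and non-lesional AA skin, we will use RT-PCR, and gene-arrays".

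**The concern.** The SALT score is total percentage scalp hair loss, so 100% involvement leaves no uninvolved scalp. A procedure required of every subject could then not be done in someone whom the design summary appears to admit. The Introduction itself calls the disease "characterized by non-scarring hair loss that can sometimes progress to total loss of all scalp and body hair", so such candidates are foreseeable.

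Two readings are possible:

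- If patchy rules out total loss, Criterion 5 and the biopsy rule agree, and the 100% in the design summary overstates the range studied.
- If patchy does not rule it out, the uninvolved-scalp biopsy is impossible in some eligible subjects, and the protocol states no exception.

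Two screeners could decide differently on the same candidate. The lesional versus non-lesional comparison, which bears on the hypothesis that IL-13 is involved in the disease, could then rest on fewer subjects than were enrolled, with those having the most extensive disease under-represented.

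**Working it through.** The plan states no figure for this point, so the check is mainly a comparison of the texts, followed by a bound on the loss of precision.

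**1. Do the limits conflict?** The design summary gives 30% to 100%. Criterion 5 gives at least 30%, and a percentage cannot exceed 100%. The numeric ranges are the same. The tension comes only from the word patchy and from the biopsy of uninvolved scalp.

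**2. Which text governs entry?** Study Design makes progress to Baseline depend on meeting all inclusion and exclusion criteria. Criterion 5 is therefore operative and the opening sentence is a summary. On the ordinary sense of patchy, some hair remains, which fits the uninvolved-scalp biopsy. On that reading the only loose item is the top figure of the summary range.

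**3. Which endpoints need the uninvolved sample?**

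| Endpoint or step | What it uses | Uninvolved scalp needed? |
|---|---|---|
| Primary: change from baseline in skin markers | Involved-site biopsy at Baseline; biopsy near that site at Week 24 or Early Termination | No |
| SALT percentage change and SALT50 | SALT at Baseline (at least 30, so the ratio is defined) and Week 24 | No |
| AASIS, AA-QoL | Questionnaires | No |
| SCORAD, EASI, IGA | Clinical scores in subjects with atopic dermatitis | No |
| Randomization | Follows the Baseline assessments, including biopsies | No |
| Lesional versus non-lesional expression | Both Baseline scalp biopsies | Yes, but not a listed endpoint |

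**4. How large could the loss be?** Let k be the number of enrolled subjects with total scalp loss. Uninvolved scalp in such a subject is 100% − 100% = 0%, so at most 30 − k pairs exist. The documents do not give k, so the values below are assumptions. For a paired mean, the 95% half-width is SD × t(0.975, n−1)/√n. The SD cancels in a ratio if it is the same at each n.

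| Planned pairs | Pairs left | t(0.975, n−1)/√n | Ratio to planned |
|---|---|---|---|
| 30 | 30 | 0.3734 | 1 |
| 30 | 29 (k = 1) | 0.3804 | 0.3804/0.3734 = 1.02 |
| 30 | 27 (k = 3) | 0.3956 | 0.3956/0.3734 = 1.06 |
| 30 | 24 (k = 6) | 0.4223 | 0.4223/0.3734 = 1.13 |
| 15 (one stratum) | 15 | 0.5538 | 1 |
| 15 (one stratum) | 14 | 0.5774 | 0.5774/0.5538 = 1.04 |
| 15 (one stratum) | 13 | 0.6043 | 0.6043/0.5538 = 1.09 |

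These ratios apply to a strictly paired analysis. Mechanistic Studies Data Analyses also names a mixed-effect model in the limma framework. Such a model can keep a lesional sample that has no non-lesional partner. That subject adds less to the contrast but need not be dropped.

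**The case for a change.** The strongest case for a change is that the wording really is inconsistent and nothing elsewhere settles it. The 100% is explicit, patchy is undefined, and the biopsy is required of all subjects. The Schedule of Events footnotes other conditional procedures, such as scores for atopic dermatitis only and optional Week 12 biopsies, yet not this one. The lesional versus non-lesional comparison is the first analysis named in the mechanistic section and bears on the primary hypothesis. A correction would take a few lines and add no visits or biopsies.

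The textual part of this stands: a careful reader will notice the mismatch, and a one-line clarification would be harmless. The consequence does not stand. To reach the troublesome reading, a site must both discount the word patchy and enrol someone in whom a required Baseline procedure cannot be done. The Introduction's remark on total loss is background on the disease, not a statement of who is eligible. The concern that the most extensive disease is left out has little force. A subject with no uninvolved scalp has no within-subject contrast to measure, and the lesional sample can still enter the mixed model.

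**Conclusion.** The inconsistency is real but clerical, and it calls for no change to the plan. On the ordinary reading, the top figure of a summary range is too generous and the protocol otherwise works as written. On the other reading, the site finds at Baseline, before allocation, that there is no uninvolved scalp, records the sample as unavailable, and the analyst reports how many pairs contributed. Writing that down would not alter what is done.

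The primary endpoint, all secondary and exploratory endpoints and the randomized comparison are unaffected on either reading. The supporting comparison could lose some pairs. Under the assumed losses of 1, 3 or 6 of 30, a paired interval widens by factors of 1.02, 1.06 and 1.13, and the true loss may be none.

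This conclusion rests on two assumptions: that the listed criteria govern entry, as Study Design states, and that the mixed-effect model is fitted to all available samples. If only paired t-tests were used, the ratios above would apply in full and would still be small. Whether total scalp loss is eligible is for the sponsor to say; no position is taken on it here.
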